9.9. Safety Analysis

All patients who received at least one dose of fexinidazole will be included in the safety analyses.

The percentage of patients with SAEs and/or AEs leading to treatment discontinuation will be presented by system-organ class, using appropriate MedDRA preferred terms, according to NCI CTCAE, version 4.03.

The percentage of patients with at least one AE will be described. If a patient experienced several AEs described using the same preferred term, the AE with the maximum severity will be used in the analysis of severity. For recurrent AEs, the frequency of occurrence of the AEs by patient will be presented. In addition, each SAE will be presented in a narrative describing all aspects of the medical event.

AEs not leading to treatment discontinuation will be presented for each treatment group using the same classification as presented above.

The incidence of SAEs and AEs, along with the respective 95% confidence intervals will be presented for the entire population, by stratum, by category and by frequency. In other cases, only descriptive statistics will be presented.

Laboratory safety parameters, i.e. haematology and biochemistry, will also be presented individually, indicating the percentage of patients, the size of the increase in the value in relation to the ULN and baseline value, and changes in blood levels over time. Shift tables will be presented. A listing of patients with laboratory abnormalities will be provided.

ECG abnormalities will be presented at each timepoint and for each stratum.

9.10. Other Analyses

PK Data

- Fexinidazole, M1 and M2 concentrations in whole blood and CSF, as well as PK parameters derived from a population PK model.
- Analysis of all PK samples will be centralised. A population PK model will be developed using Nonmem software. The model will be fitted on rich sampling data from phase-I studies and used for sparse sampling data from phase-II studies. The model will be used to estimate population PK parameters, including clearance (CL) and volume of distribution (Vd). All of the analyses and statistical methods, including data conventions, will be described in detail in a separate SAP, which will be finalised prior to database lock.
- Correlations between blood and CSF concentrations will be described on samples collected at the EOT visit. Correlations between blood and CSF concentrations, on the one hand, and the success rate/AE rate, on the other hand, will be described.

ECG Data

- QT/QTcF interval (mean, range and categories) at the various timepoints.
- Prolongation of QT/QTcF interval in relation to baseline.

All of the analyses and statistical methods, including data conventions, will be described in detail in a separate SAP, which will be finalised prior to database lock.

10. Steering Committees

10.1. Data and Safety Monitoring Board

A Data and Safety Monitoring Board (DSMB) consisting of at least 3 members independent from the Investigators and Sponsor, will be set up prior to study initiation. The DSMB will monitor the study in order to ensure that any harm to the patients included in the study is minimized. The DSMB will review safety data at pre-determined intervals, review all information related to the occurrence of SAEs and AEs leading to treatment discontinuation, and issue recommendations about the study if the current benefit-to-risk ratio for patients in the study seems to be unfavourable. The data and intervals will be agreed prior to, or soon after, study initiation and documented in the DSMB Charter.

The organisation of the DSMB and its operating methods will be described in the DSMB Charter, which will have been prepared and approved at the first meeting.

The DSMB of the pivotal study, DNDiFEX004, will also be in charge of studies DNDiHATFEX005 and DNDiHATFEX006.

Additional *ad hoc* members may be invited to join the DSMB if any safety concerns emerge, in order to give additional support to the competencies already present.

10.2. Pre-database Lock Review Committee

A pre-database Lock Review Committee, comprised of persons involved in the conduct of the study and data processing, will be responsible for assessing the consistency of the rules used to define patient disposition:

- per-protocol patients versus major violations;
- success versus failure.

11. Quality Assurance and Quality Control Procedures

The Investigator must maintain appropriate accurate records to ensure that all aspects of conducting the study are fully documented, and that study data can be verified at the end of the study. These documents include the Investigator Site File, the patients' clinical source documents, screening/enrolment logs and other study-specific forms.

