	The lumbar puncture at D11, and therefore the PK analysis on cerebrospinal fluid was stopped in October 2014 after approximately 30 patients, as initially planned in the protocol.
Study Design	This is an open-label, single-group, multicentre, Phase II/III study. The study will be a plug-in to the pivotal study, DNDiFEX004, and will be performed at the same sites.
Inclusion and Exclusion	Inclusion criteria:
Criteria	 Signed informed consent form from one parent or from the legal representative
	 Assent from the child to participate in the study, collected in the presence of an impartial witness
	 Between 6 and 15 years of age
	 Body weight at least 20 Kg
	 Male or female
	 Able to ingest at least one complete meal per day (or at least one sachet of Plumpy'Nut[®])
	 Able to swallow the 600-mg tablets of fexinidazole
	 Karnofsky score > 50
	 Evidence of trypanosomes in blood and/or lymph and/or cerebrospinal fluid.
	 Having a permanent address and able to comply with the schedule of follow-up visits.

Exclusion Criteria:

- Refusal to participate in the study, expressed by child
- Body weight strictly less than 20 Kg;
- Severe malnutrition, defined as Body Mass Index < 16. (-2 standard deviation);
- Unable to take medication by the oral route;
- Pregnancy or breast-feeding ;
- Clinically significant medical condition (other than HAT) that could, in the opinion of the Investigator, jeopardise the patient's safety or interfere with participation in the study, including, but not limited to significant liver or cardiovascular disease, suspected or proven active infection (including HIV infection), CNS trauma or seizure disorder, coma or consciousness disturbances;
- Severely deteriorated general status, including as a result of cardiovascular shock, respiratory distress or end-stage disease;
- Any condition (excluding HAT-specific symptoms) that affects the patient's ability to communicate with the Investigator as required to complete the study;
- Any contraindication to imidazole drugs, i.e. known hypersensitivity to imidazoles;
- Prior treatment for HAT in the previous 2 years;
- Prior enrolment in the study or prior intake of fexinidazole;
- Foreseeable difficulty complying with follow-up, including family of migrant workers, refugee status, itinerant trader, etc.;
- Active alcohol or drug addiction.
- Clinically significant laboratory test abnormality, with:

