• Per-protocol population: all patients with no major protocol violations that could interfere with the efficacy analysis. Sensitivity analyses will be performed on treatment completers, the population of evaluable patients and the per-protocol population. **Analysis** The primary analysis will be performed on the ITT population, by estimating the rate of success or failure at 12 months of follow-up. If the lower bound of the 95% confidence interval is less than or equal to 80% the study will be a failure, otherwise it will be a success. The primary test is an exact test derived from the exact confidence interval of the success rate at 12 months. Sample Size Determination of the sample size was based on the primary analysis. The sample size must be 125 patients having received at least one dose of fexinidazole. The sample size may be 126 patients if two patients are recruited simultaneously at the time of study discontinuation, however, it must not exceed 126 patients.

1. Background and Study Rationale

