5.7. Anonymity

This is an open-label study. All persons involved in the study will know what treatment is been administered. The patient's identity will be coded, but not for the team of care-givers and the study monitors.

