9.1. Sample Size Determination

Determination of the sample size was based on the primary analysis (see Section 9.8.1 Primary Efficacy Analysis, p 61). With a sample size of 125 patients, the probability of rejecting H_{0A} ($\pi \le 0.8$) is 97.5% if the true success rate is 92% with a one-sided type-I error of 0.025. The probability of rejecting H_{0B} ($\pi \ge 0.92$) is also 97.5% if the true success rate is 80% with a one-sided type-I error of 0.025. The statistical power achieved is slightly higher than the desired power, and the alpha value obtained is slightly lower than the desired value, due to the discrete distribution of the population. The sample size may be 126 patients who received at least one dose of fexinidazole if two patients are recruited simultaneously at the time of study discontinuation. If the sample size exceeds 126 patients, there is a risk of simultaneously rejecting both H_{0A} and H_{0B}. The sample size should not be less than 125 in order to avoid the risk of not rejecting either hypothesis.

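### Unblinded study staff review the success/failure rules before lock, with a one-child pass mark and no stated analysis of the outcome as it stood before that review

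*Protocol*

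**What the plan says.** Section 10.2 of the protocol sets up a review committee before database lock, "comprised of persons involved in the conduct of the study and data processing". It "will be responsible for assessing the consistency of the rules used to define patient disposition", under two items: per-protocol status, and "success versus failure". The section mentions no independent member, no charter, no masking to the running count and no record of changed outcomes. Section 10.1, by contrast, requires the DSMB to be independent of investigators and sponsor and to work under a charter.

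On design, the Protocol Summary says: "This is an open-label, single-group, multicentre, Phase II/III study". Section 5.7 adds: "All persons involved in the study will know what treatment is been administered".

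On the decision rule, the Summary says: "If the lower bound of the 95% confidence interval is less than or equal to 80% the study will be a failure". Section 9.8.1 turns this into counts: success from 109 of 125 (110 of 126), failure below that.

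On the outcome, section 9.8.1 requires no trypanosomes and CSF WBC of at most 20/µL. A higher count, or an investigator's view that rescue is needed, makes the child a failure. Table 1 (section 5.9) has a 12-month column for probable success that includes some children with counts above 20/µL.

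On sensitivity analyses, section 9.8.2 varies the analysis set and leaves further analyses to the SAP. Section 9.2 adds two other ways of handling missing outcomes.

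**The concern.** In a single-arm trial no control group exists in which a lean in borderline classifications could cancel out. Any lean goes straight into the primary estimate. The people who review the success/failure rules took part in the study, know the treatment and can read the pass mark in the protocol. There is no middle zone: one child separates a failed study from a successful one.

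The rules under review also leave something to decide, because two places in the protocol label the same child differently. If the outcome before review is not kept and analysed, a reader of a narrow result cannot tell whether the verdict depended on the review.

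**Working it through.** **Inputs.** N = 125, or 126 (section 9.1); unacceptable rate 80%, target 92%, exact test, cut-off 109/125 or 110/126 (section 9.8.1); one-sided alpha 0.025 (section 9.1).

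**1. The plan's own figures.** Section 9.1 starts from "With a sample size of 125 patients" and says that the probability of rejecting the 80% null "is 97.5% if the true success rate is 92% with a one-sided type-I error of 0.025". With X ~ Bin(n, p) and cut-off r, the chance of success is P(X ≥ r) = Σ C(n,x) pˣ(1−p)ⁿ⁻ˣ over x = r to n.

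| N, cut-off | Type I error at 80% | Power at 92% | P(study failure) at 80% |
|---|---|---|---|
| 125, 109 | 0.0243 | 0.9781 | 0.9757 |
| 126, 110 | 0.0220 | 0.9765 | 0.9780 |

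The stated figures reproduce.

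**2. The boundary.** The exact 95% limits are the 2.5% quantile of Beta(x, n−x+1) and the 97.5% quantile of Beta(x+1, n−x).

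| Count | Rate | 95% CI | Verdict |
|---|---|---|---|
| 108/125 | 86.4% | 79.12% to 91.87% | failure |
| 109/125 | 87.2% | 80.05% to 92.50% | success |
| 109/126 | 86.5% | 79.28% to 91.94% | failure |
| 110/126 | 87.3% | 80.20% to 92.56% | success |

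One child reverses the verdict, but only from a count next to the boundary.

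**3. How often one child matters (N = 125).** A reversal upward needs X = 108 exactly.

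| True rate | P(X = 108) |
|---|---|
| 80% | 1.8% |
| 87% | 10.2% |
| 88% | 8.9% |
| 90% | 4.6% |
| 92% | 1.1% |

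The chance that the count is one to three short (106 to 108) is larger: 26.9% at 87%, 21.9% at 88%, 9.5% at 90% and 2.0% at 92%. That is relevant only if up to three children are moved.

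**4. Effect on type I error.** Assume that one failure can always be moved to success when needed. The effective cut-off becomes 108, and at a true 80% the error is 0.0243 + P(X = 108) = 0.0243 + 0.0179 = 0.0422. With two children it is 0.0690, with three 0.1068. These are worst cases, not predictions.

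**5. Where the rules differ at 12 months.**

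| Child without trypanosomes or rescue | Section 9.8.1 | Table 1 |
|---|---|---|
| CSF WBC above 20/µL, rise regarded as not clinically significant | failure | probable success |
| CSF WBC above 20 and below 50/µL, lower than before | failure | probable success |

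A ruling on which label feeds the primary endpoint settles the outcome of every such child.

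**6. Would a changed outcome show?**
- No lumbar puncture at 12 months or later: the second method of section 9.2 sets the child to failure, so a call of probable cure is undone there.
- Lumbar puncture done and outcome changed: the second method does not apply, and the analysis sets of section 9.8.2 change who is counted, not how. The changed outcome stays in every stated analysis of the 12-month endpoint that includes the child.

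**The case against.** The strongest reply concerns the remit. The committee is asked to check the consistency of rules, not to adjudicate children, and no section gives it power to change an outcome. A reader might infer from section 10.2 that staff may reclassify children. The text does not say so. What stands is narrower: the text does not exclude it, and where the rules conflict a ruling on them fixes individual outcomes.

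A reader might also infer that a changed outcome would leave no trace at all. The documents do not support that either. The second imputation method exposes children without a puncture, section 11.2 requires discrepancies with source documents to be accounted for, section 11.7 requires queries to be documented, and section 4.1 has microscope images stored. These protect the data, but none yields a second primary estimate.

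Third, the endpoint is largely objective, and the investigator's opinion on rescue can only turn a child into a failure. Table 1 is headed as clinical management, not as the endpoint definition. Both points are fair and limit the number of doubtful cases, but they do not remove the difference over counts above 20/µL.

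Last, pre-lock review by trial staff is ordinary practice, a printed cut-off is good prespecification, and listings or derivation programs usually belong in the SAP, which is not available here and may already contain such an analysis. That is why this is a modest improvement and not an error. The committee's composition and remit, however, are fixed in the protocol itself.

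**Conclusion.** The point holds in a limited form. Unblinded study staff review the success/failure rules before lock in a single-arm trial with a one-child boundary, and the protocol states no analysis of the outcome as classified before that review. For children with a lumbar puncture, a change would pass unnoticed through the stated analyses.

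The size is modest. One child moved up matters about 10% of the time if the true rate is near 87%, and about 1% of the time at the 92% target. The rise in type I error from 2.4% to 4.2% assumes that a movable child always exists and is always moved; nothing in the protocol shows that any lean would occur. The figures for a shortfall of one to three children should not be read as the risk from a single reclassification. The conclusion also assumes that the SAP adds no analysis on unreviewed outcomes.

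**What to change.** Amend section 10.2 to state that:
- the 12-month outcome is derived by program from the section 9.8.1 definition, using the investigator's opinion as recorded in the CRF, and is frozen before the committee meets;
- the committee works from listings without centre or running total;
- every outcome changed at review is listed with its reason;
- the primary estimate and exact interval are reported with both the frozen and the reviewed outcome, and the text names in advance which of the two decides the verdict.

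Before the program is written, reconcile Table 1 with section 9.8.1 for outcome classification of children with CSF WBC above 20/µL. Which clinical rule applies is for the sponsor and investigators to settle.

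The cost is one extra listing and one repeated estimate, with no new staff and no change to sample size or visits. If both results agree, a narrow success is easier to defend.

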11.1. Investigator Site File

The Investigator's Site File must contain the protocol and protocol amendments, IEC and regulatory approval with all correspondence, a copy of the patient information and informed consent form, drug accountability records and

curriculum vitae for study personnel, as well as authorisation forms and any other relevant documents or correspondence.

11.2. Case Report Forms

Data will be collected by laboratory technicians, physicians, nursing staff or caregivers authorised by the Investigator. Data collection will be supervised by the Investigator. Study-specific information will be entered in a case report form (CRF). Data generated from this information must be consistent with the source documents, and any discrepancies must be accounted for. Some data may be collected directly in the CRF, in which case, this will be described in the Investigator manual. All data that are recorded in the CRF must be rendered anonymous, i.e. such that they are only identified by the patient's code.

The Investigator must ensure the accuracy, completeness, legibility and timely entry of all data reported to the Sponsor via the CRF, and any other additional information that is requested. The Investigator is responsible for ensuring that all informed consent forms and screening forms for all patients are stored in a secure location. Data will be entered in the CRF after each patient visit. The CRF will be signed by the Investigator.

11.3. Source Documents

The data in the CRF must be verified by direct inspection of the source documents. The source documents are the patients' medical files, the physicians' and nursing staff's notes, appointment books, originals of laboratory test results, ECG tracings, reports on specific assessments, signed informed consent forms and patient screening/enrolment logs. Some data collected directly in the CRF may be considered as source data, in which case the data concerned will be described in detail in the Investigator Manual.

The Investigator must keep the source documents up to date, i.e. reports on laboratory tests and consultations, records of medical history and physical examination reports, so that they can be examined and/or audited by DND*i* or its designated clinical monitors and/or by the Regulatory Authorities.

11.4. Retention of Documents

The Investigator must retain all essential documents for at least two years after approval of the last marketing authorisation is obtained, and until there are no ongoing or planned applications for marketing authorisation, or until at least 15 years after the official stop date of clinical development of fexinidazole. However, study documents may need to be retained for a longer period of time if required by local regulations in effect or by agreement with DND*i*. It is the responsibility of the Sponsor to inform the Investigator/institution as to when these documents no longer need to be retained. After that date, the documents may be destroyed with prior permission from DND*i*, subject to local regulations.

DND*i* must be notified in advance if the Investigator plans to assign the study records to another party or move them to another site.

11.5. Monitoring

Clinical monitors will perform regular monitoring visits during which they will verify source data, Informed Consent Forms, medical records, laboratory results, imaging reports, CRFs, drug dispensing logs and protocol violations. The monitors will be given access to the corresponding source documents for each patient on condition that that the patient's confidentiality is maintained in accordance with local regulations.

Monitoring visits at the investigational sites will be performed periodically by *DNDi* representatives or designated clinical monitors to ensure compliance with Good Clinical Practice and all aspects of the protocol. Source documents will be reviewed for verification of consistency with the data in the CRFs. It will be the clinical monitor's responsibility to inspect the CRFs at regular intervals. The Investigator will ensure that DND*i* designated representatives have direct access to source documents. It is important that the Investigators and the personnel concerned are available during monitoring visits. The Investigator agrees to cooperate with the clinical monitor to ensure that any problems detected during monitoring visits are resolved.

The monitoring visits provide DND*i* with the opportunity to assess progress of the study, to verify the accuracy and completeness of the CRFs and to resolve any inconsistencies in the study records, as well as to ensure compliance with all protocol requirements, applicable regulations and Investigator obligations.

Four types of visits are planned: site evaluation visit, site initiation visit, monitoring visit and site closure visit.

11.6. Audits and Inspections

The investigational centres may also be subject to quality assurance audits by DND*i* or designated representatives, and/or to inspection by regulatory authorities or IEC members.

The purpose of the inspections is to verify adherence to the protocol and to ensure the study is being conducted in accordance with Good Clinical Practice. It is important that the Investigators and the personnel concerned are available for any audits or inspections.

11.7. Data Management

A CRF must be completed for each patient who has given informed consent. The present clinical study will use a CRF. The study data will be stored in a computer database maintaining confidentiality in accordance with national legislation on data protection.

All data will be entered in the CRF under the responsibility of the Investigator or a qualified designated staff member.

Data will be reviewed by the clinical monitor. Data queries will be generated, documented and resolved on a regular basis throughout the study.

11.8. Confidentiality of Information, Study Documents and Patients' Files

The Investigator will ensure that the anonymity of patients is maintained and that their identity is protected from unauthorised third parties. Patients must not be identified by their names in the CRF or on any other documents submitted to the Sponsor. Only the patient number should appear. The Investigator must keep a patient enrolment log containing the patients' number, name and address. The Investigator must ensure the confidentiality of all documents submitted to the Sponsor's authorised representatives, including the signed informed form.

The findings of any assessments, including laboratory tests, will remain strictly confidential to the patient him/herself. This includes patients under legal age and vulnerable patients. Particular attention will be paid to the confidentiality of the results of pregnancy tests and tests related to concomitant diseases.

12. Protocol Amendments

The Investigators will ensure that the study is conducted in strict compliance with the protocol, and that all data are collected and recorded in the CRF.

All protocol modifications must be documented in writing. A protocol amendment can be initiated by either the Sponsor or any Investigator. The Investigator will provide the reasons for the proposed amendment in writing and will discuss it with the Sponsor and the Principal Investigator.

Any protocol amendment must be approved and signed by the Sponsor and the Principal Investigator, and must be submitted to the appropriate IEC for information and approval in accordance with local requirements, and to regulatory agencies, if required. Approval must be received from the IEC, and the regulatory authorities, if applicable, before any changes can be implemented, with the exception of changes required to avert an immediate risk for study participants, or when the change involves only logistical or administrative aspects of the study, e.g. changes in telephone numbers.

13. Early Termination of Study

Both the Sponsor and the Principal Investigator will have the right to terminate the study early, i.e. at any time prior to inclusion of the planned number of patients, but they may exercise this right only for valid scientific or administrative reasons. If this is necessary, the two parties will define the procedures for terminating the study after consultation. The Sponsor and the Principal Investigator will ensure that early termination of the study takes place in such a way as to protect of the patients' interests.

Reasons for which the study may be terminated by the Sponsor include, but are not limited to:

- insufficient enrolment rate;
- protocol violations;
- inaccurate or incomplete data;
- dangerous or unethical practices;
- on recommendation from the DSMB or IEC.

Reasons for which the study may be terminated by the Investigator include, but are not limited to:

- insufficient time or resources to conduct the study;
- lack of eligible patients.

If the study is terminated early by the Sponsor or the Investigator, the latter must:

- complete all CRFs to the largest extent possible;
- return all study-related articles and equipment to the Sponsor who provided them;
- answer all queries from the Sponsor, or delegated representatives, related to data on patients enrolled by the site prior to study termination;
- ensure that patients enrolled in the study who have not yet attended any follow-up visits receive all necessary medical care;
- provide the IEC, the regulatory authorities and, if appropriate, the Sponsor with a written explanation of the decision to terminate the study.

14. Ethical Considerations

The protocol for this study was prepared in accordance with the general ethical principles set out in the Declaration of Helsinki of the World Medical Association (see Appendix 1 – Declaration of Helsinki; p 83) and ICH guidelines for Good

Clinical Practice (ICH Harmonised Tripartite Guideline - Guideline For Good Clinical Practice E6(R1) - current step 4 version, dated 10 June 1996). DNDi commits to respect all applicable laws for the protection of the rights and welfare of human subjects.

The protocol will be officially submitted by the Principal Investigator for approval from the IEC of the Ministry of Health of the DRC (Clinique Ngaliema).

Approval from the IEC must be received prior to undertaking any protocol-specific procedure in any patient.

In addition, the protocol will be reviewed by the MSF Ethics Review Board prior to study initiation in the sites concerned, since MSF is involved in the study as an implementation partner.

Any modification made to the protocol after receipt of the IEC approval must also be submitted in writing by the National Investigator to the IEC, in accordance with local procedures and regulatory requirements (see Section 12 Protocol Amendments, p 69).

The protocol will be submitted along with appendices relevant to the information and safety of patients, such as the patient information sheet & consent/assent form, and the Investigator Brochure. The set of images provided to the Investigators as visual aids to explain the study procedures will be presented to the IEC. The patient information sheet and consent/assent form should be formally agreed upon by each IEC separately.

The protocol will be submitted for opinion from the IEC of Necker Hospital in Paris, France.

